#### 9.4. Adjustment for Multiplicity

Two endpoints will be subject to multiplicity adjustment: The primary endpoint (achievement of a 30% reduction in WOMAC pain)

This will be accomplished by first testing for significance of the two active doses of XT-150 versus placebo with respect to the primary endpoint at the 0.025 level, one-sided. This addresses the multiplicity of doses with respect to the primary endpoint. Then a Dunnett test for the 50% endpoint will be performed at the alpha remaining after having done the first Dunnett test. Using only the remaining alpha for this additional endpoint continues to control the overall false positive rate at 0.025, one-sided. The numerical value of this remaining alpha depends on the primary (30% endpoint) Dunnett test as follows:

[figure not shown]
- If both doses are significantly better than placebo, then the remaining alpha is the full 0.025 level.
- If exactly one of the two active doses is significantly better than placebo, then the alpha remaining will be determined by the software performing the primary Dunnett test. (If the statistical analysis was of Gaussian group means, with N=90 per group, the remaining alpha would be 0.0115 (one-sided); the actual alpha may be different, because the model includes a covariate and the sample sizes may not be exactly 90 per group.)
- If neither active dose is significantly better than placebo, then no alpha remains and no inferential testing will be performed.

Achievement of a 30% improvement in WOMAC Pain score at Day 180 will be analyzed using a logistic regression model as described in Section 9.3 to preserve a familywise error rate of 0.05 (two-sided),

#### 10. CHANGES FROM THE ANALYSIS PLANNED IN THE PROTOCOL

Although the protocol called for step-down statistical testing using the Dunnett approach, the Dunnett testing will not use step-down testing, because it would exhaust the 'alpha' available for additional statistical testing. By not using the step-down approach, it is permissible to continue statistical testing provided that at least one of the treatment arms is statistically significantly different from the control group, with respect to the primary endpoint.

CONFIDENTIAL Page 20 of 27

Protocol No.: XT-150-2-0204 Sponsor: Xalud Therapeutics, Inc.

#### 11. DATA LISTINGS AND SUMMARY TABLES

#### 11.2. Listings and Tables for Clinical Study Report

The data listings and summary tables, and associated figures, planned to be generated from the study data are listed in Appendix 1 and Appendix 2, respectively. The numbering and titles may vary in the final presentation, depending on the amount of data to be presented.

Listings, tables and figures will be provided to the Sponsor in a form suitable for inclusion as appendices to the Clinical Study Report, in RTF or PDF format. The layout will be landscape A4 size, with a margin of 1 inch. The default font for listings and tables will be Courier New 8 pt.

In the summary tables other than those included in the main text of the report, special characters and formatting will not be used. For example, units will be shown as ug ( $\mu$ g) and m^2 (m²).

Data in listings will be ordered by subject, then date/time.

#### 11.3. Data Transfer to the Study Sponsor

At the conclusion of the study, will provide the Sponsor with an electronic copy of the listings, tables and figures, along with analysis data sets in SAS transport format and XPT format. This may be provided by email or by upload, as determined by the Sponsor.

Details of the statistical analyses will be retained in the

#### 12. GENERAL CONSIDERATIONS FOR DATA MANAGEMENT AND ANALYSIS

#### 12.1. Analysis Packages

SAS 9.4 or higher (SAS Institute Inc., Cary, NC, USA) will be used for generating data listings and summary tables and associated figures, and for performing statistical analysis.

#### 12.2. Electronic Data Management

All listings, tables and figures for inclusion in the appendices of the clinical study report will be generated using SAS programs.

CONFIDENTIAL Page 21 of 27

[figure not shown]

Final 2.0, 11 Oct 2021

Protocol No.: XT-150-2-0204 Sponsor: Xalud Therapeutics, Inc.

A copy of final listings, tables and figures will be retained in the internal study file. A tracking log will be maintained detailing the date and initials of the staff member responsible for generating each listing, table or figure, and the staff member conducting the quality control review. Any erroneous results identified during subsequent checking process will be corrected by update of the SAS program, and the document recreated and then re-checked. To ensure an accurate data trail is maintained, corrections to electronic documents will be included on the tracking log, detailing the correction along with the date of the new version as well as the initials of the staff member responsible for the change and the verifying staff member. If statistical analysis is repeated with a modified data set, the new data produced will be saved as a new file.

#### 12.3. Archiving

CONFIDENTIAL Page 22 of 27

Final 2.0, 11 Oct 2021

Protocol No.: XT-150-2-0204 Sponsor: Xalud Therapeutics, Inc.

#### **Appendix 1: Planned Data Listings**

The following listings and figures of individual subject data are planned to be created, however the numbering and titles may vary, depending on the amount of data to be presented. Data presentation in listings may vary depending on CDISC datasets.

CONFIDENTIAL Page 23 of 27

Final 2.0, 11 Oct 2021

Protocol No.: XT-150-2-0204 Sponsor: Xalud Therapeutics, Inc.

CONFIDENTIAL Page 24 of 27

[figure not shown]

Final 2.0, 11 Oct 2021

Protocol No.: XT-150-2-0204 Sponsor: Xalud Therapeutics, Inc.

#### **Appendix 2: Planned Summary Tables**

The following summary tables are planned to be created, however the numbering and titles may vary, depending on the amount of data to be presented:

Final 2.0, 11 Oct 2021

Protocol No.: XT-150-2-0204 Sponsor: Xalud Therapeutics, Inc.

CONFIDENTIAL Page 26 of 27

Final 2.0, 11 Oct 2021

Protocol No.: XT-150-2-0204 Sponsor: Xalud Therapeutics, Inc.

CONFIDENTIAL Page 27 of 27

#### Introduction

This Statistical Analysis Plan (SAP) Addendum describes the planned analyses to be done in addition to the primary analyses defined in the primary study SAP. The analyses planned in this SAP addendum were defined after the study database was locked and unblinded. Therefore, these analyses are considered post hoc analyses. However, these analyses can provide important supportive evidence of efficacy for the purposes of planning future studies and for understanding the effectiveness of XT-150 in subjects with moderate to severe pain due to osteoarthritis of the knee.

The focus of the analyses planned in this SAP Addendum is to characterize the efficacy during Stage B of the study (after Day 180 to Day 360) and to assess the effects of the second injection of XT-150.

Due to the exploratory nature of these analyses, no adjustments for multiplicity will be made.

SAS v9.4 or higher (SAS Institute Incl, Cary, NC, USA) will be used for all programming and analyses as well as to produce the summary tables and figures.

#### **Analysis Populations**

The following analysis populations will be used for the post hoc efficacy analyses:

**Intent-to-Treat Population (ITT)**: The Intent-to-Treat population will consist of all randomized subjects who received at least one treatment injection. ITT population is analyzed based on the treatment to which subjects are randomized.

**Modified Intent-to-Treat Population (mITT)**: The Modified Intent-to-Treat population will consist of ITT population who received at least one treatment injection with a baseline WOMAC Pain score of 9-20 (>8). This is the target population of interest who may benefit most from the treatment.

#### **Analysis Sets**

We will further separate the analyses into analyses for Stage A and Stage B:

- Stage A (up to and including Day 180) data on first injection. This is the primary analysis for efficacy.
- Stage B (>Day 180 to Day 360) data on second injection. The second injection could be taken at any time the patient decided, at Day 180 through Day 330.

#### **Treatment Groups**

The following descriptions define the treatment groups (or regimens) that will be used in the analyses:

- Stage A (up to and including Day 180): Subjects were randomized to placebo, 150 μg
   XT-150 or 450 μg XT-150 during Stage A. For the Stage A analyses each dose of XT-150 will be compared to placebo at Day 180:
  - o 150 μg XT-150 vs Placebo
  - o 450 μg XT-150 vs Placebo.
- Stage B (> Day 180 to Day 360): Subjects were randomized to receive either 150 μg XT-150 or 450 μg XT-150 during Stage B. The following treatment regimens will be compared for the Stage B analyses:

[figure not shown]
- o 1 Dose 450 vs 2 Dose 450
  - Placebo to 450 vs
  - **450** to 450
- o All Dose Regimens
  - Placebo to 150
  - 150 to 150
  - **450 to 150**
  - Placebo to 450
  - 150 to 450
  - **450** to 450

## Baseline

Baseline will be defined as the Day 0 value for both Stage A and Stage B analyses.

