- f. Participant assessment will be recorded in response to the question: "Considering all the ways the OA in your knee affects you, how are you doing today?" on a scale of 1 to 5, 5 being worst
- i. Women of child-bearing potential
- Verify that the participant meets all study inclusion and exclusion criteria before enrollment as close to study drug dosing as
 possible.
- k. Participant will receive a single, 1-mL dose of study drug into the intra-articular space of the knee on Day 0. Participant may elect a second injection on Day 180 (enters Stage B) after efficacy assessments have been recorded.
- A telephone call documenting safety and efficacy assessments may be used for participants unable to physically attend follow
 up visits due to COVID-19 infection or corona virus exposure concerns

Table 2. Schedule of Assessments and Procedures - Stage B

Scheduled Event	Follow up Visit Day ^d							
	210	240	270	300	330	360		
	(±7)	(±7)	(±7)	(±7)	(±7)	(±7)		
KOOS/WOMAC	X	X	X	X	X	X		
BPI	X	X	X	X	X	X		
Patient response to OA question	X	X	X	X	X	X		
	X	X	X	X	X	X		
						X		
Brief physical examination	X	X	X	X	X	X		
Record height and weight, calculate BMI						X		
Vital signs	X	X	X	X	X	X		
Clinical exam of the treated joints	X	X	X	X	X	X		
Record AEs	X	X	X	X	X	X		
Record SAEs	X	X	X	X	X	X		
	X	X	X	X	X	X		
Record concomitant medications	X	X	X	X	X	X		
Serum for anti-IL-10 antibody assessments						X		
Serum pregnancy test ^b						X		
Administer study drug ^c	X	X	X	X	X			

Footnotes to Table 2

- b. Women of child-bearing potential
 c. Participants may elect for one (1) XT-150 IA injection into the Index Knee at any point during Stage B up to Day 330, inclusive. The XT-150 dose (150 μg or 450 μg) will be randomly assigned.
- d. A telephone call documenting safety and efficacy assessments may be used for participants unable to physically attend follow up visits due to COVID19 infection or corona virus exposure concerns

$\mathbf{T}A$	BLE OF CONTENTS	
PF	OTOCOL SYNOPSIS	3
TA	BLE OF CONTENTS	10
	ST OF ACRONYMS, ABBREVIATIONS AND DEFINITIONS (
	RMS	
	CKGROUND AND RATIONALE	
4.1	XT-150	
4.2		
4.3	1	
4.4		

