#### 4.4. Study Treatment

Treatments in Stage A:

- Placebo (1 mL phosphate-buffered saline for injection)
- 150 μg XT-150 (1 mL)
- 450 μg XT-150 (1 mL)

Treatments in Stage B:

- 150 μg XT-150 (1 mL)
- 450 μg XT-150 (1 mL)

At enrolment in Stage A, participants will be randomly enrolled into 1 of 6 treatment sequences (approximately 45 participants/ group) to receive one of 3 treatments in Stage A, and, optionally, one of 2 treatments in Stage B.

CONFIDENTIAL Page 8 of 27

Final 2.0, 11 Oct 2021

Protocol No.: XT-150-2-0204 Sponsor: Xalud Therapeutics, Inc.

At any time in Stage B up to Day 330, inclusive, participants can elect for a single injection to the knee dosed in Stage A (Index Knee). The second injection dose will be either 150  $\mu$ g or 450  $\mu$ g XT-150, according to the randomized treatment sequence allocated on enrolment in Stage A. There will be no placebo comparator in Stage B.

Treatment sequences for randomization:

- XT-150 (150 μg) in Stage A, followed by XT-150 (150 μg) in Stage B
- XT-150 (150 μg) in Stage A, followed by XT-150 (450 μg) in Stage B
- XT-150 (450 μg) in Stage A, followed by XT-150 (150 μg) in Stage B
- XT-150 (450 μg) in Stage A, followed by XT-150 (450 μg) in Stage B
- Placebo in Stage A, followed by XT-150 (150 μg) in Stage B
- Placebo in Stage A, followed by XT-150 (450 μg) in Stage B

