## 4. Efficacy Analyses

The following efficacy endpoints will be analyzed as described below:

- WOMAC Pain Score Change from Baseline at Day 360
- WOMAC Function Score Change from Baseline at Day 360

• BPI Interference Change from Baseline at Day 360

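### The SAP Addendum's Day 360 contrasts compare assigned sequences and cannot be read as the effect of a second injection at a defined time after dosing

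*SAP*

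**What the plan says.** The Introduction to the SAP Addendum gives part of its focus as "to assess the effects of the second injection of XT-150". The rules that bear on this are:

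- **Optional dose.** Protocol Table 2, footnote c: "Participants may elect for one (1) XT-150 IA injection into the Index Knee at any point during Stage B up to Day 330, inclusive". Under SAP 4.4, each participant is randomised at enrolment to one of six sequences, receiving one of three treatments in Stage A "and, optionally, one of 2 treatments in Stage B".
- **Timing.** Addendum, Analysis Sets: "The second injection could be taken at any time the patient decided, at Day 180 through Day 330".
- **Baseline.** Addendum, Baseline: "Baseline will be defined as the Day 0 value for both Stage A and Stage B analyses".
- **Endpoint.** Addendum, Efficacy Analyses: "WOMAC Pain Score Change from Baseline at Day 360". WOMAC Function and BPI Interference follow the same pattern.
- **Population and grouping.** Addendum, Analysis Populations: "The Intent-to-Treat population will consist of all randomized subjects who received at least one treatment injection", and "ITT population is analyzed based on the treatment to which subjects are randomized". The mITT set adds only a baseline WOMAC Pain threshold.
- **Model and displays.** The mixed model reports Day 180 and Day 360, with site, baseline score, K/L grade and sex as covariates. Summaries and the line plot run by study visit and treatment group.

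Regimens are named by the assigned pair of treatments. One contrast, Placebo to 450 against 450 to 450, is labelled as one 450 µg dose against two.

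**The concern.** The question concerns the second injection, but the clock starts at the first. Baseline, endpoint and displays all follow study day from Day 0, and no listed covariate records whether or when the second injection was given. Two participants with the same label and the same Day 360 visit may be one month and six months past their second dose. A third with that label may have had no second dose.

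The Addendum offers these results as supportive evidence for planning future studies. A planner needs to know how large the effect of re-dosing is and how long after the dose it appears. If the Day 360 contrasts are taken as that answer, a difference could reflect the first injection, the timing of requests or who asked. Equally, the absence of a difference could reflect low uptake or averaging over very different intervals.

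**Working it through.** The Addendum states no sample size, power or uptake for Stage B, so it offers no figure to reproduce. The power table in Protocol 13.1 and SAP 4.5 concerns Day 180 response and has no bearing here.

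**1. Time from second injection to the Day 360 assessment.** Inputs: injection from Day 180 to Day 330 (Addendum, Analysis Sets); visits at Days 180, 330 and 360, each ±7 days (Protocol Tables 1 and 2).

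- Nominal: 360 − 330 = 30 days to 360 − 180 = 180 days, a six-fold range.
- Longest with windows: 367 − 173 = 194 days.
- Shortest with windows, Day 330 as a hard cap: 353 − 330 = 23 days.
- Shortest if the Day 330 visit window also applies to dosing: 353 − 337 = 16 days.

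For a participant who never took the injection, the interval is undefined.

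**2. Scores recorded before the injection.** A participant injected at Day 300 contributes Days 210, 240 and 270 to the summaries and plot under a two-injection label, although only one injection had then been given. This affects the by-visit displays. By Day 360, everyone who will take the second injection has taken it.

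**3. Participants without a second injection.** The ITT set requires one injection, which the Day 0 dose satisfies, and groups by randomised treatment. Read literally, a 450 to 450 group can include people given 450 µg once, and a Placebo to 450 group can include people never given XT-150. With about 45 per sequence (SAP 4.4) and uptake u, the number without the second injection is 45 × (1 − u). Uptake is an assumption throughout:

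| u | Without second injection, of 45 | Share of a recipient-level difference retained |
|---|---|---|
| 0.9 | 4.5 | 90% |
| 0.75 | 11.25 | 75% |
| 0.5 | 22.5 | 50% |
| 0.25 | 33.75 | 25% |

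The last column applies u × D, where D is the mean 150 versus 450 µg difference at Day 360 among recipients. It holds only when both groups share a Stage A arm, as with placebo/150 against placebo/450. The second dose is then pre-assigned and blinded, so uptake and timing should be alike in the two groups.

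**4. Contrasts across Stage A arms.** For Placebo to 450 against 450 to 450, let F be what remains at Day 360 of the first 450 µg injection. Let u₁ and u₂ be uptake in the two groups, and S₁ and S₂ the mean benefit at Day 360 of the Stage B injection in each group's recipients, averaged over their own dosing times. Then

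difference (450 to 450 minus Placebo to 450) = F + u₂S₂ − u₁S₁.

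If uptake, timing and benefit match, this reduces to F, a first-injection quantity. If requests depend on the Stage A arm or on response to it, the last two terms do not cancel and their net direction is unknown. No single uptake factor corrects this.

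**The case against.** Four objections carry weight.

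- **Recipients only.** The Analysis Sets section describes the Stage B set as second-injection data, which may mean recipients only. Text is also missing from the public copy around the treatment-group list and the planned analyses, and it may hold a rule. A reader might infer that the Addendum definitely counts undosed people as re-dosed; the visible text does not settle that. Under the recipients-only reading, step 3 falls away but the spread in time since dosing remains. Comparisons across Stage A arms would then rest on a choice made after randomisation.
- **Day 0 baseline.** A reader might call it an error. It is not: it precedes randomisation and suits a comparison of assigned sequences. The fault lies in reading that comparison as the effect of the second injection.
- **Uptake is already partly covered.** SAP 9.3 analyses time to request for a second injection, and SAP 7.1 lists administration and summarises exposure. What is missing is uptake and injection day by sequence.
- **Limited stakes.** The Addendum declares itself post hoc, exploratory and unadjusted for multiplicity. Nothing here touches the Day 180 primary analysis, and it would be wrong to infer otherwise.

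There is also a caution about any remedy. Participants may ask for re-dosing when pain is high, so within-group change from a pre-injection score invites regression to the mean.

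**Conclusion.** The mismatch between purpose and analysis is real. The Day 360 contrasts compare assigned sequences. They cannot be read as the effect of a second injection at a defined time, because that time ranges nominally from 30 to 180 days, and this part needs no assumption about uptake.

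Whether undosed participants are included depends on how the Addendum is meant to be read, and it must say. The size of any dilution is unknown: within a shared Stage A arm it is roughly 1 − u, for instance 20% to 50% lost at an assumed u of 0.8 to 0.5. That figure should not be carried over to contrasts across Stage A arms.

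This is worth correcting before the results inform a new trial, but it is not a defect in the trial's main result.

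**What to change.** - **Keep** the ITT and mITT Day 360 analyses with the Day 0 baseline, labelled as by assigned sequence regardless of whether the second injection was taken. State whether Stage B means all ITT participants or recipients only.
- **Add** an analysis among recipients, with visits re-indexed by days since the second injection. Compare the randomised 150 and 450 µg second doses, adjusting for Stage A arm and the last score confirmed as recorded before the injection. Protocol 9.6 puts the Day 180 assessments before dosing, but 9.7 gives no order for later visits, so the Addendum needs a rule for same-day scores.
- **Report** about 30 days, which every recipient can nominally reach, together with later time points so that durability is not lost. Give the number contributing at each.
- **Report** uptake and day of injection by sequence.

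The cost is Addendum wording and a re-derived visit variable. Injection dates are recorded (Protocol 8.6), KOOS and BPI are collected at every Stage B visit (Protocol Table 2), and SAP 5.5 already derives time since the Stage B dose for adverse events. No new data are needed.

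The downside is that recipient groups are smaller and self-selected. The 150 versus 450 µg comparison stays randomised as long as the blind held, because the dose was assigned at enrolment. Comparisons across Stage A arms within recipients are not randomised, and within-group change is open to regression to the mean. The added analysis would be post hoc like the rest of the Addendum.

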## Planned Analyses

[figure not shown]
## 4. Efficacy Analyses

The following efficacy endpoints will be analyzed as described below:

- WOMAC Pain Score Change from Baseline at Day 360
- WOMAC Function Score Change from Baseline at Day 360

• BPI Interference Change from Baseline at Day 360

#### **WOMAC Pain Score Change from Baseline**

WOMAC Pain Score Change from Baseline will be summarized with summary statistics by visit and treatment group. Analyses will be performed for both the ITT population and mITT population.

A Mixed Model analysis will be conducted and mixed model statistics (LSMean, StErr, LSMeans Diff and 95% CI of LSMeans diff) – generated for Day 180 and Day 360 (covariates include site, baseline WOMAC Pain, K/L and sex). The effect size at Day 180 and Day 360 using Cohen's d will be calculated from the observed mean and standard deviations and presented.

A summary line plot of WOMAC Pain Mean Change from Baseline by visit and treatment group (with Standard Error at each visit) will be generated.

The following additional exploratory analyses will be performed for the WOMAC Pain Change from Baseline using the same MMRM model to compare treatment groups:

• Stage B (Day 360) analyses comparing treatment groups placebo/150 and placebo/450 to assess the difference between these groups and the assumption of combining them for the placebo/active treatment group.

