9.6 Follow up Visit – Stage A, Day 180 [±7 days)

- Clinical assessments
 - o Brief physical exam, including the injection site for infections or inflammation
 - o Measure vital signs (temperature, heart rate, blood pressure, and respiratory rate)
- Efficacy assessments
 - Record BPI scores (Appendix 2)
 - Record KOOS scores (Appendix 3)
 - O Record participant's response to the question: "Considering all the ways the OA in your knee affects you, how are you doing today?" on a scale of 1 to 5, 1 being very good (asymptomatic and no limitation of normal activities) to 5, very poor (very severe, intolerable symptoms and inability to carry out normal activities)
 - Record changes in drug regimens or pain therapy

- Laboratory assessments: Obtain serum for analysis of anti-IL-10 antibodies
- · Assess, identify, and record any AEs since last visit
- Record any changes in concomitant medications since screening visit including prescription, OTC, and herbal medications.
- Refresh training on accurate pain reporting

At participant's option, administer a second injection to the Index Knee after Day 180 efficacy and safety assessments have been recorded. The second injection will be XT-150 active drug, randomly assigned to be either 150 μg or 450 μg. Record reason provided by the participant for requesting the second injection.

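### The addendum's placebo/150 v placebo/450 comparison at Day 360 makes no visible use of the Day 180 score and is probably less precise than it could be

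*SAP*

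**What the plan says.** The SAP addendum sets one baseline for everything: "Baseline will be defined as the Day 0 value for both Stage A and Stage B analyses". Under WOMAC Pain Score Change from Baseline, the mixed-model statistics are "generated for Day 180 and Day 360 (covariates include site, baseline WOMAC Pain, K/L and sex"). The same section adds "Stage B (Day 360) analyses comparing treatment groups placebo/150 and placebo/450 to assess the difference between these groups", "using the same MMRM model to compare treatment groups", and says this bears on combining the two sequences. The Function and BPI Interference sections repeat the same analyses with their own baseline scores.

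The Analysis Sets section describes Stage B as "Stage B (>Day 180 to Day 360) data on second injection", which leaves Day 180 itself outside the set. It adds: "The second injection could be taken at any time the patient decided, at Day 180 through Day 330".

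Two facts lie elsewhere. SAP 4.4 (Study Treatment) randomises each participant at enrolment to one of six sequences, so the second dose is fixed before Day 0. Protocol 9.6 places the option to "administer a second injection to the Index Knee after Day 180 efficacy and safety assessments have been recorded", and Table 1 schedules KOOS/WOMAC at that visit.

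**The concern.** The placebo/150 and placebo/450 sequences receive the same treatment until the second injection. A difference between them at Day 180 can therefore only be chance. The Day 180 score is likely to predict Day 360 better than a Day 0 score taken a year earlier. A model that adjusts only for Day 0 variables leaves the chance Day 180 difference in the Day 360 contrast.

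The stake is modest but specific. The contrast has about 45 v 45 participants at most, and it is meant to inform pooling. A wide interval here could make pooling look harmless when it is not, or show an apparent dose difference that was already present before the second injection. The addendum's Introduction says its results may help plan future studies.

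**Working it through.** **Group size.** SAP 4.4 gives about 45 per sequence, and 270 / 6 = 45. The addendum states no standard deviation, standard error, interval width or power for these contrasts, so there is no other plan figure to reproduce.

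**Validity of the covariate.** The dose is assigned at enrolment, and the Day 180 score is taken before any second injection. The assigned second dose therefore cannot affect it. This holds between sequences with the same Stage A treatment. It fails for placebo/450 v 450/450, where Day 180 is an outcome of the first injection.

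**Precision in SD units.** Let a, b and c be the Day 0–Day 180, Day 0–Day 360 and Day 180–Day 360 correlations. None is in the documents, so all are assumed.

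- Day 0 only: R² = b².
- Day 0 and Day 180: R² = (b² + c² − 2abc) / (1 − a²).
- SE ratio = √[(1 − R² with both) / (1 − R² with Day 0)].
- 95% half-width = 1.96 × √(2/45) × √(1 − R²) = 0.413 × √(1 − R²).

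| a, b, c | R², Day 0 | R², both | SE ratio | Half-width, SD |
|---|---|---|---|---|
| 0.3, 0.2, 0.4 | 0.04 | 0.167 | 0.93 | 0.41 → 0.38 |
| 0.3, 0.3, 0.5 | 0.09 | 0.275 | 0.89 | 0.39 → 0.35 |
| 0.4, 0.3, 0.6 | 0.09 | 0.364 | 0.84 | 0.39 → 0.33 |
| 0.4, 0.4, 0.7 | 0.16 | 0.507 | 0.77 | 0.38 → 0.29 |

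First row in full: (0.04 + 0.16 − 0.048) / 0.91 = 0.167, and √(0.833 / 0.96) = 0.93. Simulation at 45 v 45 (4,000 runs) gave 0.94, 0.91, 0.85 and 0.76. Formula and simulation together give a reduction of about 6% to 24%. In sample-size terms, 0.96 / 0.833 = 1.15 and 0.84 / 0.493 = 1.70, so the gain is worth about 15% to 70% more participants.

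**Precision in points.** Let r be the partial correlation of the Day 180 and Day 360 scores given the Day 0 covariates. The SE is multiplied by √(1 − r²): 0.95, 0.87 and 0.71 for r = 0.3, 0.5 and 0.7. Assume a residual SD of 4 to 5 points on the 0–20 scale (not in the documents) and 45 per group. The half-width 1.96 × SD × √(2/45) is 1.65 to 2.07 points. It falls to 1.58–1.97, 1.43–1.79 or 1.18–1.48. If only 20 per group contributed, at SD 5, it would fall from 3.10 to 2.68 (r = 0.5) or 2.21 (r = 0.7).

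**Does the MMRM already use Day 180?** This depends on terms the addendum does not state. A 2,000-replicate simulation covered r = 0.3, 0.5 and 0.7. With complete data and free group-by-visit means, including Day 180 as an outcome gave the same Day 360 standard error as adjusting for Day 0 alone (ratio 1.000). Adding Day 180 as a covariate gave 0.96, 0.87 and 0.72. With 20% of Day 360 scores missing, the free-means MMRM reduced the standard error by 1% to 7%, and the covariate by 3% to 31%. A material gain therefore needs either the covariate or a common Day 180 mean.

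**The case against.** The addendum says openly that it was written after unblinding, is post hoc and exploratory, and makes no multiplicity adjustment. Randomisation makes the planned contrast unbiased, and its 95% interval already allows for chance Day 180 differences. That stands: a reader might infer a biased comparison or an inflated error rate, and the documents support neither.

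The reach is narrow. Placebo/150 v placebo/450 is the only same-arm pair named as a contrast. The pairs 150/150 v 150/450 and 450/150 v 450/450 appear only as members of a list of regimens. A reader might conclude that second-dose comparisons are affected throughout, but the text does not go that far.

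The model is only partly visible. Material is missing under Planned Analyses and Treatment Groups, and the wording of the covariate list does not exclude others. The addendum uses three groups for Stage A and six regimens for Stage B. If one model followed that grouping, the placebo sequences would share a Day 180 mean and most of the gain would already be present. It would therefore be too strong to say that the MMRM cannot benefit from Day 180. That conclusion needs free group-by-visit means and complete data, and the addendum specifies neither.

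The size is also uncertain. Site, K/L and sex may absorb part of the gain. Some participants are re-dosed months after Day 180, so that score is pre-dose but not the latest. The 45 per group is planned enrolment. The planned by-visit summaries would show a Day 180 imbalance, though they would not remove it from the Day 360 estimate.

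All of this limits the size and scope of the point. None of it removes the point, because no visible text adds Day 180 as a covariate or constrains the Day 180 means.

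**Conclusion.** The point holds as a minor, optional improvement. For placebo/150 v placebo/450 at Day 360, and the same contrast for Function and BPI Interference, the visible plan does not use a valid predictor that is already collected. If the two sequences are not given a common Day 180 mean, the contrast is less precise than it could be.

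Under assumed Day 180–Day 360 correlations of 0.4 to 0.7 and Day 0–Day 360 correlations of 0.2 to 0.4, the standard error falls by about 6% to 24% at 45 v 45. The half-width falls from 0.38–0.41 SD to 0.29–0.38 SD. Even the best case leaves the pooling check imprecise, and the visible text gives no criterion for pooling.

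**What to change.** For placebo/150 v placebo/450, and for 150/150 v 150/450 and 450/150 v 450/450 if those are tested, add one of two models:

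- a separate Stage B model with only post-Day-180 visits as outcomes and the endpoint's Day 180 score as a covariate beside the Day 0 score; or
- a model that keeps Day 180 as an outcome and constrains sequences sharing a Stage A arm to equal means through Day 180.

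The Day 180 covariate should not simply be added to the existing model, which reports Day 180 as an outcome. Neither version should be used across Stage A arms, such as placebo/450 v 450/450. Because the addendum postdates unblinding, report the new model beside the existing one rather than in its place, and state the group-by-visit terms of both.

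The cost is one further exploratory model per endpoint on data already collected. Participants without a Day 180 score drop out of the covariate version; the constrained version keeps them.
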